#### **Aim 2. To determine whether a novel awe intervention improves subjective experience and reduces symptoms in older adults**

#### **Methods**

### ***Awe Walk Intervention***

After the laboratory assessment, participants will be randomized into one of two 8-week conditions: (1) awe condition or (2) control condition. All participants will be instructed to take a weekly 15-minute walk. In the awe condition, participants will be instructed to pay attention to the vastness and novelty of the environment around them. In the control condition, participants will receive no additional instructions.

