### ***Post-Intervention Follow-Up Assessment***

At the conclusion of the 8-week intervention and at 3- and 6-months post-intervention, participants will again complete the physical and mental health questionnaires that they completed during their baseline visit.

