Effects of Awe on Health

11/22/2016

IRB approval date: 11/22/2016

8.25 STATISTICAL METHODS: Briefly summarize the methods and types of analyses that will be performed:

We will conduct multiple regression analyses to determine whether the laboratory measures of emotional reactivity (i.e., ANS reactivity, facial expression, and self-reported experience) are associated with mental health symptoms such as anxiety and depression. We expect that greater negative emotional reactivity as

measured in the laboratory will be associated with worse mood and higher anxiety.

We will use mixed effects models to test whether the awe walk condition had beneficial effects on daily self-reported experience, life satisfaction, and prosociality. We will use analyses of covariance (controlling for age, sex, and education) to examine whether the awe walk condition resulted in decreases in anxiety and depression at the termination of the 8-week intervention and at 3- and 6-months post-intervention.

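### The planned ANCOVAs of anxiety and depression have no missing-data rule, so as normally run they ignore the week-8 scores of people who stop responding before 3 or 6 months

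*SAP*

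**What the plan says.** The protocol (Awe Walk Intervention) states that "participants will be randomized into one of two 8-week conditions". Under Post-Intervention Follow-Up Assessment the mental health scales are repeated three times after baseline: "At the conclusion of the 8-week intervention and at 3- and 6-months post-intervention, participants will again complete the physical and mental health questionnaires". So each responder can supply a baseline score and up to three later scores on the same anxiety and depression instruments.

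SAP 8.25 assigns two different methods. For the diary: "We will use mixed effects models to test whether the awe walk condition had beneficial effects on daily self-reported experience, life satisfaction, and prosociality". For the scales: "We will use analyses of covariance (controlling for age, sex, and education"). The stated purpose of the latter is: "examine whether the awe walk condition resulted in decreases in anxiety and depression at the termination of the 8-week intervention and at 3- and 6-months".

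Neither document names an analysis population, an imputation rule, a sensitivity analysis or a longitudinal model for anxiety and depression. The covariate list includes neither the baseline score nor any earlier follow-up score.

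**The concern.** An ANCOVA of a given visit's score needs that score for each person. With the listed covariates there is no route by which a week-8 score can inform the 6-month comparison. A participant who completes the walks and the week-8 scales and then stops replying therefore counts at week 8 and, by default, disappears at 3 and 6 months. If the plan instead means a single repeated-measures ANCOVA with the usual listwise deletion, that person is lost from the week-8 comparison as well.

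These ANCOVAs are the only planned comparison of anxiety and depression between conditions, and the last one falls 6 months after the walks end. If the chance of stopping depends on week-8 symptoms differently in the two arms, a comparison of remaining responders mixes the treatment effect with a difference in who remained. If it does not, the cost is mainly precision. In both cases the change between visits is harder to interpret when the set of people contributing can change from visit to visit.

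**Working it through.** **Inputs from the documents.** Two randomised arms; scales at baseline, week 8, 3 months and 6 months; ANCOVA with three demographic covariates; mixed models for diary outcomes only. There is no stated sample size, alpha, power, SD, correlation or dropout rate, so there is no figure of the plan's to reproduce.

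**Assumed inputs.** Scores with SD 1; equal correlation r = 0.5 or 0.7 between any two visits; N = 50 or 100 in total; about 20% or 30% lost by 6 months, in two steps (after week 8 and after month 3). Dropout depends on the week-8 score with logit slope b = 0.7 (odds multiplied by e^0.7 = 2.0 per SD) in the awe arm and not in the control arm. No true effect. Age, sex and education are not modelled.

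**Step 1: responders only, no baseline.** To first order, a dropout probability p at each step shifts the mean week-8 score of those who remain by -b × 2p. The 6-month score inherits r times that shift, so the bias is about r × b × 2p in favour of awe.
- 20% lost: p = 1 - √0.8 = 0.106. With r = 0.5: 0.5 × 0.7 × 0.211 = 0.07 SD.
- 30% lost: p = 1 - √0.7 = 0.163. With r = 0.7: 0.7 × 0.7 × 0.327 = 0.16 SD.

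Simulation gives the same range, 0.07 to 0.16 SD. A likelihood estimate that uses the week-8 scores of those lost is biased by about 0.01 SD or less.

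**Step 2: baseline score added to the ANCOVA.** The bias becomes about r(1 - r) × b × 2p, that is, (1 - r) times Step 1.
- r = 0.7, 20% lost: 0.21 × 0.7 × 0.211 = 0.03 SD.
- r = 0.5, 30% lost: 0.25 × 0.7 × 0.327 = 0.06 SD.

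Simulation gives 0.03 to 0.06 SD. Baseline adjustment thus removes a fraction r, or 50% to 70%, of the bias, but not all of it.

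**Step 3: change from baseline as outcome.** The expected 6-month minus baseline difference, given week-8 score y, is r·y - r·y = 0. Under equal correlations the bias vanishes; with unequal correlations it need not.

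**Step 4: symmetric loss.** The same slope in both arms shifts both means equally, so under no effect the bias is about zero. The likelihood estimate then has a standard error 2% to 7% smaller without baseline and about 1% to 2% smaller with it.

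**Step 5: other patterns.** A separate simulation assumed 50 per arm, a true effect of -0.40 SD, slope 1.0 and nominal loss of 10% to 30% after week 8. The estimate using week-8 scores stayed at about -0.40 throughout. Responders only gave:
- loss unrelated to scores: -0.40, with variance 2% to 18% larger;
- symptom-related loss, same slope in both arms: -0.36 to -0.38;
- symptom-related loss in controls only: -0.30 to -0.33 at 10% nominal loss, -0.25 to -0.29 at 20%, -0.19 to -0.24 at 30%.

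The direction therefore depends on which arm loses its more symptomatic members.

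**Step 6: scale against noise.** For Step 1 the standard error is about √(2/40) = 0.22 (50 per arm, 20% lost) to √(2/17.5) = 0.34 (25 per arm, 30% lost). At the worst point, 50 per arm with 30% lost, 0.16/√(2/35) = 0.67 standard errors. The two-sided 5% error rate becomes P(Z > 1.29) + P(Z < -2.63) = 0.099 + 0.004 = 0.10. Simulated error rates were 0.05 to 0.10 without baseline and 0.05 to 0.06 with it.

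**The case against.** Section 8.25 answers a form item that asks for a brief summary. It does not say that each visit is analysed separately or that only responders are included, and an ANCOVA can be run after imputation. A reader might infer that the plan prescribes three responders-only analyses. The text does not support that: it is the usual result of the named method when no missing-data rule is given. This objection limits the wording, but brevity does not supply the missing rule.

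The stated aim of testing for decreases could also mean that change from baseline is the outcome, in which case Step 3 gives no bias under equal correlations. That stands as a reason not to present 0.07 to 0.16 SD as the plan's expected error.

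The bias also needs symptom-related loss that differs by arm. Both arms take the same weekly walk and complete the same questionnaires, and nothing in the documents points to such an asymmetry. Finally, much of the adverse case is cured simply by adding the baseline score, after which the error rate is close to nominal. Both points are correct. What remains for the mixed model is a few hundredths of an SD and 1% to 2% of the standard error, at almost no cost.

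**Conclusion.** The concern holds in a limited form. The named method, with no missing-data rule, makes no use of week-8 (or 3-month) scores from people lost later, and a better method of a type already in the plan is available. Its size is conditional on inputs the documents do not give: about 0.07 to 0.16 SD at 6 months under no effect with one-sided symptom-related loss, 0.03 to 0.06 SD once baseline is adjusted for, and about zero with symmetric loss or with change scores under equal correlations, where the gain is mainly modest precision.

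Three stronger conclusions might be drawn, and none is supported:
- That the later results will show a false benefit of awe. The direction depends on an unknown dropout pattern.
- That late loss is especially likely in this trial. No retention figure is given.
- That a fading effect could not be told from a change in responders. Reporting who remained at each visit, or a completers' comparison, would help to separate them.

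**What to change.** In SAP 8.25, for each anxiety and depression scale, replace the ANCOVAs with one likelihood-based mixed model of the week-8, 3-month and 6-month scores. Terms: condition, visit, condition by visit, baseline score, baseline by visit, age, sex and education, with unstructured within-person covariance. Include every randomised participant with at least one post-randomisation score, in the assigned arm. Requiring one such score still excludes anyone lost during the 8 weeks; modelling baseline as an outcome instead keeps all randomised participants. Read each visit's effect from the model's contrasts, keep the per-visit ANCOVA as a sensitivity analysis, and report the numbers contributing at each visit.

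Cost: a few sentences of SAP text and slightly more analysis; no new data, since the baseline scales are already collected. The model estimates a few more covariance parameters, and it relies on missingness being explained by observed scores. That is a weaker assumption than the complete-case ANCOVA makes, but it does not cover loss that depends on scores never seen. With no dropout the change costs and gains essentially nothing beyond the baseline adjustment.
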